Telehealth virtual reality gaming on cardiometabolic health among youth with cerebral palsy

NCT05336227 FEB 14, 2024

Background:

While there is a wealth of evidence demonstrating that exercise can improve cardiorespiratory fitness, musculoskeletal muscle strength and function, and gross motor skills (1-4), there are fewer than a handful of studies that have demonstrated improvements in cardiometabolic health in youth with cerebral palsy (YwCP) (e.g., body weight, blood pressure, lipids, and blood glucose or insulin) (5-8). Improvements to cardiometabolic health generally require regular participation in moderate-to-vigorous intensity exercise over at least a 1-3 month time frame (9, 10). This time commitment creates a need for exercise modalities that can successfully engage youth with disabilities in sustained exercise participation in their community, without the supervision by a clinician or specialist.

To address this gap, this exploratory pilot trial (NCT05336227) adapted the latest "off-the-shelf" virtual reality (VR) head-mounted displays to promote a usable health-enhancing volume of exercise among youth with cerebral palsy (YwCP). The study also included fully remote telehealth procedures to overcome common barriers to exercise such as lack of time and transportation, in the hopes of addressing a second critical gap in the literature: small sample sizes that prevent generalizable study findings (1-4).

Objectives:

- 1) Examine the preliminary efficacy of a 12 week, of home-based VR exercise training compared to a waitlist control group on indicators of cardiometabolic health and physical activity participation among YwCP.
- 2) Assess the feasibility of the program by evaluating safety, recruitment, adherence rates, and implementation challenges.
- 3) The tertiary purpose of the study is to generate a theory that reveals critical behavioral mechanisms of adherence to tele-exergaming.

Methods

Design

This study was a pilot randomized controlled trial with a 2-armed parallel group design, comparing an immediate start (IS) group versus a waitlist control (WC) group, where the wait group underwent their normal daily routines and activities (11).

Participants

Participants were recruited locally from a Children's hospital and nationally through the Cerebral Palsy Foundation. The study was conducted from a single site and utilized completely remote procedures to allow participants to complete the study from their home. Inclusion criteria included a medical diagnosis of cerebral palsy, Gross Motor Function Classification System (GMFCS) level between I-IV, between the ages of 13-24 years (rationale: youth age range and the minimum age required for using the VR headset), and a physician's clearance to participate. People were excluded if they were physically active (>150 minutes per week of moderate-to-vigorous intensity exercise in a typical week); classified as GMFCS level V; completely blind or deaf; and had contraindications to exercise.

Randomization, Sample Size, and Other Trial Considerations

Participants provided digital consent and assent through REDCap prior to participation. Participants were randomized with a 1:1 allocation ratio using a permuted block randomization approach. Participants were stratified based on their GMFCS level. The randomization sequence was generated by the project statistician using a computer-generated random schedule in permuted block (SAS V.9.4; SAS Institute). The project recruiter and outcome assessor were blinded to group allocation. The study started on June 6th, 2022, and the primary completion date was November 1st, 2024. Sample size determination was based on a power *estimate* calculation using a noncentral T distribution approach that is intended for pilot RCTs (11).

Seated Virtual Reality Exercise

The intervention included exergaming using a Meta Quest head-mounted display. The Quest 2 was used until the release of the Quest 3 (October 2023). Participants received accessories to enhance accessibility, if comfort and accessibility were identified as an issue in the first intervention week. Accessories included a controller knuckle strap to accommodate people who were unable to grip or hold onto the controllers and head strap to enhance comfort by relieving frontal face or neck pressure and increasing the ease of equipping the device. For exercise, participants received consumer-available fitness games with rhythmic movements, which often included music. Participants were asked to exercise as possible each week, with a minimum goal of 150 min/week of moderate-intensity exercise and an advanced goal of 300 min/week of moderate-intensity exercise (further details can be found elsewhere)(12). Participants received a heart rate monitor (Polar OH1) to record their average exercise heart rate during each session, using an app from the Android and Apple Play Store (VR Health or VR Health Exercise Tracker). The participant or their caregiver took a screenshot after each exercise session and sent the screenshot to the study telecoach. When receiving a screenshot, the telecoach would respond with an inspiring emoji or verbal praise. The telecoach also provided weekly, theory-based, behavioral coaching and technical assistance through brief phone calls (~10 minutes) and text messages (12). Participants in the wait control group received the same intervention, after waiting for a 12-week period with their normal daily activities.

Procedures and Outcomes

Quantitative data were collected 3 times: baseline (week 0), mid-intervention or wait (week 7), and post-intervention or wait (week 13). A qualitative interview was conducted in week 13. All assessment procedures were conducted remotely, with study outcomes detailed elsewhere (12).

Purpose 1: Blood-related Cardiometabolic Health.

Cardiometabolic health indicators included fasting insulin (µIU/mL), hemoglobin A1c (mmol/mol), high-sensitivity C-reactive protein (hsCRP; mg/L), fasting triglycerides (mg/dL), fasting cholesterol (mg/dL), and resting blood pressure (mmHg). These outcomes were measured by the participant and caregiver at home using a dried blood spot test kit, which was mailed to study staff and then mailed to the ZRT laboratory for analysis (12). Body weight was measured using a conventional bathroom scale that was shipped to participants. Blood pressure was measured using a sphygmomanometer (Omron 3 Series).

Purpose 1: Physical Activity Participation.

Self-reported activity was measured via the Godin Leisure Time Exercise Questionnaire (GLTEQ) at weeks 0, 7, and 13. The GLTEQ is a 7-day recall survey, scored using a health contribution metric, where only the moderate and vigorous components were scored using a multiplier of 5 and 9, respectively, and summed. An HC score of \geq 24 can equate to the minimum aerobic guideline of 150 mins/week of moderate exercise (13, 14).

Purpose 2: Feasibility Metrics.

Metrics included recruitment and adherence rates, trial management challenges related to technology and telehealth procedures, and intervention safety, assessed through number of adverse events (e.g., falls or injuries or problems) and potential intervention effects on pain and fatigue (measured by NIH Neuro-QoL Pediatric short forms)(12).

Analyses

As a preliminary study, the study is not powered for effectiveness. Findings will inform sample size and design considerations for an effectiveness trial. Analyses were performed in an intent-to-treat manner.

Primary Aim

Descriptive statistics (means and SDs) were used to summarize participant baseline characteristics, and baseline variables were compared between groups using one-way analysis of variance. The primary analyses were conducted in an intent-to-treat manner, using linear mixed-effects models to compare between-and within-group changes (IS or WC). Models included fixed effects for the treatment group (IS vs. WC), time (baseline, week 7, and week 13), and their interaction. Random effects were included for participants to account for individual variability. Optimal model selection was based on Akaike's Information Criterion. Post hoc analyses were conducted using least-squared mean differences and 95% confidence intervals (CI). Mixed models for repeated measures data effectively handled missingness in outcomes, supplemented by multiple imputations by chained equation in Stata (StataNow/SE 18.5). Multiple imputations were performed by including outcomes, time, and auxiliary variables with 10 iterations. Estimations were combined using Rubin's rules (the STATA *mi* procedure). Blood spot specimens that were delayed longer than four weeks in the mail were excluded (due to potential degradation of the sample when not stored in ultra-low temperatures), resolved by missing imputation. Analyses were conducted using SAS software (version 9.4), with statistical significance set at p < 0.05.

Secondary Aim

For the feasibility metrics (ie, recruitment, retention, and adherence rates), no a priori criteria for acceptability will be established. Questionnaire results will be descriptively reported, and changes across time will be explored using general linear mixed models techniques, such as mixed models repeated measures analyses. An appropriate structure for the covariance matrix (eg, unstructured) will be selected for these models using the final data. Post hoc analyses will be performed using the Tukey-Kramer multiple comparisons test.

Tertiary Aim

The qualitative component will follow Charmaz's constructivist grounded theory framework, guided by the following philosophical assumptions: critical realism ontological perspective and an interpretivism epistemological perspective. Data will be analyzed by two investigators. Data

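### Randomisation is stratified by GMFCS level, but the primary model lists no GMFCS term; the interval for between-group change is too wide if GMFCS predicts change

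*Combined protocol and SAP*

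**What the plan says.** The Randomization, Sample Size, and Other Trial Considerations section describes the allocation: "Participants were randomized with a 1:1 allocation ratio using a permuted block randomization approach", and "Participants were stratified based on their GMFCS level". Under Participants, eligibility requires "Gross Motor Function Classification System (GMFCS) level between I-IV", so there are up to four strata. Whether levels were pooled is not stated, nor is the block size.

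The Primary Aim part of Analyses describes the model as "using linear mixed-effects models to compare between-and within-group changes (IS or WC"). It then lists the terms: "Models included fixed effects for the treatment group (IS vs. WC), time (baseline, week 7, and week 13), and their interaction". It adds "Random effects were included for participants to account for individual variability", and "Post hoc analyses were conducted using least-squared mean differences and 95% confidence intervals (CI"). It does not say whether those differences are of change or between arms at a visit.

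Two other statements there might have brought GMFCS in, but neither commits to it. Model selection by Akaike's criterion is mentioned without saying what was selected. The imputation is described as "Multiple imputations were performed by including outcomes, time, and auxiliary variables with 10 iterations", with the auxiliary variables unnamed. No section explains why the stratification factor is absent from the model.

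**The concern.** Stratified allocation balances the arms on GMFCS, so outcome variation explained by GMFCS largely drops out of the true error of the treatment comparison. A model that ignores the factor still counts that variation in its estimated standard error. The design gain is real, but the reported interval does not show it.

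What is at stake is the width of the reported interval. The plan states that this pilot is not powered to show an effect, so the interval, more than the p-value, is what a reader can use from the between-arm comparison. The factor had to be known for every participant at randomisation, so using it requires no new data.

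**Working it through.** **Inputs from the documents.** Three visits (weeks 0, 7 and 13); 1:1 allocation in permuted blocks, stratified by GMFCS I-IV; fixed effects group, time and group x time; participant random effects; significance at 0.05 (two-sided assumed). The plan gives no sample size, SD, effect size or GMFCS association, so there is no figure of its own to reproduce. All R² and N values below are assumptions.

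**Step 1. Change contrast, GMFCS affects level only.** A constant GMFCS effect is the same at baseline and week 13, so it subtracts out of each participant's change. Take N = 40 (20 per arm) and residual variance 1. The change then has variance 2, and the SE of the between-arm difference is √(2/20 + 2/20) = 0.4472. Generalised least squares gives 0.4472 with no GMFCS term, with a main effect, and with GMFCS x time. In mixed-model fits to simulated complete data, adding the main effect left estimates and SEs unchanged.

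**Step 2. GMFCS also predicts change.** Add change variance 0.5 due to GMFCS, so R² = 0.5/2.5 = 0.20. The listed model reports √(2.5/20 + 2.5/20) = 0.5000. A GMFCS main effect alone still gives 0.5000. GMFCS x time gives 0.4472. The ratio is 1.118 = 1/√(1 − R²).

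**Step 3. Dependence on the covariance.** With an unstructured covariance, the listed model overstates the SE by 1/√(1 − R²). A random-intercept model pools the residual over two within-participant contrasts. If the GMFCS effect grows linearly over the visits (0, 0.5, 1), only one of the two carries it, and the ratio falls to √(1 + R²/(2(1 − R²))):

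| Change R² | Random-intercept ratio | Interval narrower by | Unstructured ratio | Interval narrower by |
|---|---|---|---|---|
| 0.1 | √1.0556 = 1.027 | 2.7% | 1.054 | 5.1% |
| 0.2 | √1.125 = 1.061 | 5.7% | 1.118 | 10.6% |
| 0.3 | √1.2143 = 1.102 | 9.3% | 1.195 | 16.3% |

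These large-sample values assume exact balance and ignore degrees of freedom.

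**Step 4. Simulation at a pilot size.** Assumed N = 30 (strata 7/6/9/8), blocks of 4, complete data, no imputation:

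| Change R² | Size without GMFCS, random intercept | CI change, four-level GMFCS x time | CI change, collapsed (I-II vs III-IV) | Size without GMFCS, unstructured | CI change, four-level |
|---|---|---|---|---|---|
| 0 | about 5% | +0.8% | +0.3% | about 5% | +1.1% |
| 0.1 | 4.3% | −2.1% | −2.0% | 3.9% | −4.4% |
| 0.2 | 3.9% | −5.3% | −4.5% | 3.1% | −10.3% |
| 0.3 | 3.2% | −9.1% | −7.4% | 2.0% | −16.5% |

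The collapsed column assumes a linear trend over levels. If level IV alone differs, collapsing narrows the interval by only 0.5%, 1.2% and 2.2% at R² of 0.1, 0.2 and 0.3.

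**Step 5. Missing visits.** With 20% missing at weeks 7 and 13, adding a GMFCS main effect changes the SE of the change contrast by +0.1% to −0.4% for level R² from 0 to 0.3. The cancellation in Step 1 is therefore exact only with complete data, but the exception is about 0.4% or less.

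**Step 6. Visit-level difference, if that is what was reported.** The interval is too wide by 1/√(1 − R²) − 1, where R² is now for level: 5%, 12% and 20% at 0.1, 0.2 and 0.3, and 0% at 0.

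**Step 7. Type I error when the covariance is wrong.** Same N = 30 design, but with errors correlated AR(1) at 0.7 (assumed) and a random-intercept fit. At R² = 0, size without GMFCS is 9.2%. At R² = 0.2 it is 7.5% without GMFCS and 9.2% with GMFCS x time. An unstructured covariance at R² = 0.2 gives 3.1% and 5.0%.

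**The case against.** The strongest reply is that no harm is shown. Nothing in the documents says that GMFCS predicts change in the blood markers, blood pressure or activity score. The exercise is seated, and accessories were supplied to improve accessibility, so such an association cannot be presumed. The study is an exploratory pilot, the intervals are introduced as post hoc, and any error from this source is conservative. This stands, and it is why the point is minor. It does not explain why a factor important enough to stratify on is missing from the listed model.

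A second reply is that the simulations are not the described analysis: they use complete data and no multiple imputation, and the size depends on the covariance model. This also stands. The percentages illustrate a range and do not estimate this trial's loss.

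A third reply is that conservatism is guaranteed only if the fitted covariance is adequate. This is correct. In Step 7 the excess over 5% comes from the covariance and not from omitting GMFCS, but adding GMFCS x time to a misspecified random-intercept model moved size further from nominal. The fix needs a covariance condition for that reason.

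**Conclusion.** The mismatch between design and listed model is real, and its consequence is minor. For between-group change with complete data, the reported standard error is too large if GMFCS predicts change, and is unaffected if GMFCS predicts level only. For a visit-level difference, it is too large whenever GMFCS predicts level. At the assumed N = 30 and change R² of 0.1 to 0.3, the four-level term would narrow the interval by about 2% to 9% (random intercept) or 4% to 16% (unstructured). The true figure is unknown and may be zero.

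A reader might infer more, but the documents do not support it:

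- **Precision is lost because GMFCS is prognostic.** This does not follow for the change contrast, where a constant effect cancels.
- **The estimator itself is less precise.** Stratification has already secured the true precision; it is the estimated standard error that is too large.
- **The estimate is biased or false positives rise.** Neither follows from the omission: with complete data there is no bias, and omission alone makes the test conservative. Nothing is claimed here about bias under missing data.
- **Size is assured to be 5% or less.** That holds only if the fitted covariance is adequate.
- **The next trial's sample size will be wrong.** The plan does not say which estimate would feed that calculation, so no such consequence is claimed.

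**What to change.** 1. State whether GMFCS was in the primary model and in the imputation, and whether the between-arm result is a difference in change or a difference at a visit.
2. If the primary analysis is not final, include GMFCS as randomised, with GMFCS x time for the change contrast. The main effect alone serves only visit-level contrasts. If levels are sparse, collapse to I-II versus III-IV, decided without reference to outcomes by arm.
3. Fit this model with a covariance that allows unequal correlations between visits, for example unstructured.
4. Include GMFCS in the imputation model.
5. If the analysis is complete, as the past tense of the Primary Aim text suggests, leave the primary model as it is and report the GMFCS-adjusted model as a labelled sensitivity analysis.

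**Cost.** No new data are needed. The listed model has 6 fixed parameters (intercept 1, group 1, time 2, interaction 2). Four-level GMFCS adds 3 + 6 = 9; the collapsed form adds 1 + 2 = 3. If GMFCS does not predict change, the interval for change widens by about 1% with four levels, or 0.3% if collapsed, at N = 30. Collapsing forfeits most of the gain if only one level differs.

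### Adverse events are specified only as a number although exercise volume is self-chosen; the share of participants affected and an exposure-based rate should be added

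*Combined protocol and SAP*

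**What the plan says.** The combined protocol and SAP defines safety under Procedures and Outcomes, Purpose 2: Feasibility Metrics. It has two parts. In the first, safety is "assessed through number of adverse events (e.g., falls or injuries or problems"). The second is "potential intervention effects on pain and fatigue (measured by NIH Neuro-QoL Pediatric short forms"). Adherence is listed in the same sentence as a separate metric.

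The section Seated Virtual Reality Exercise sets the exercise volume: "Participants were asked to exercise as possible each week, with a minimum goal of 150 min/week of moderate-intensity exercise". Beyond this lower target, the same section names a higher one: "an advanced goal of 300 min/week of moderate-intensity exercise". No fixed volume and no upper limit are stated. On session records it says: "The participant or their caregiver took a screenshot after each exercise session and sent the screenshot to the study telecoach". The waitlist arm has no intervention for 12 weeks and then receives the same programme.

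In Analyses, Secondary Aim, recruitment, retention and adherence are named without preset acceptability thresholds, and questionnaire scores get mixed models over time. Adverse events are not mentioned: there is no rate, no share of participants affected, no observation period and no summary by arm.

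**The concern.** Falls and injuries caused by play can occur only while someone is playing. If participants play little, the count is low whatever the risk per session. Low volume is plausible here, because people already active for more than 150 min/week are excluded, so everyone starts at or below the lower goal. Adherence is one of the things Objective 2 sets out to learn.

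A count has two further limits. It does not show whether the events fell on one participant or on several. Nor does it show which period it covers, which matters because the waitlist arm contributes an unexposed period followed by an exposed one.

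What is at stake is how far the safety result can be carried forward. The Analyses section says that the findings are to inform the design of an effectiveness trial. A count cannot be transferred to a trial of another size or with other adherence. A rate with an interval, read beside the percentage affected, can.

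**Working it through.** The documents give no expected number of adverse events and no numerical sample size, so there is no planned figure to reproduce. The check asks how much the meaning of one count changes with exercise volume.

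**Inputs from the document**
- Length of intervention: 12 weeks (Objective 1).
- Goals: 150 and 300 min/week (Seated Virtual Reality Exercise).

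**Assumptions, for illustration only**
- 20 exercisers (10 to 30 in the last step).
- 3 events, or none.
- A low-adherence volume of 30 min/week.
- A true rate of 1 event per 100 hours in the last step.

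**Step 1. Hours per person** = min/week × 12 / 60.
- 150 min/week: 150 × 12 / 60 = 30 h.
- 300 min/week: 300 × 12 / 60 = 60 h.
- 30 min/week (assumed): 30 × 12 / 60 = 6 h.

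The two stated goals differ by 60 / 30 = 2-fold. This ratio needs no assumption about sample size or number of events. Setting the assumed low volume against the upper goal gives 60 / 6 = 10-fold.

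**Step 2. Rate for the same 3 events** = 3 / total hours × 100, with an exact two-sided 95% Poisson interval. **Upper limit with no events** (one-sided 95%) = −ln(0.05) / total hours × 100.

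| Average min/week | Total hours, 20 people | 3 events, per 100 h (95% CI) | No events: upper limit per 100 h |
|---|---|---|---|
| 300 (goal) | 1200 | 0.25 (0.05 to 0.73) | 0.25 |
| 150 (goal) | 600 | 0.50 (0.10 to 1.46) | 0.50 |
| 30 (assumed) | 120 | 2.50 (0.52 to 7.31) | 2.50 |

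The intervals treat events as independent. They would usually be wider if events cluster within participants.

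**Step 3. Chance of seeing no events** = exp(−rate × hours), at the assumed rate of 1 per 100 h.
- 20 people at 150 min/week: exp(−6) = 0.002.
- 20 people at 30 min/week: exp(−1.2) = 0.301.
- At 30 min/week, 10 people give exp(−0.6) = 0.549 and 30 people give exp(−1.8) = 0.165.

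At the same underlying risk, a count of zero is therefore very unlikely at the lower goal and unremarkable at low adherence.

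**Step 4. Clustering.** Among 20 people, 3 events may mean 3 / 20 = 15% affected or 1 / 20 = 5% affected. The count is the same in both cases.

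**The case against.** The strongest reply is that the sentence lists what is measured and does not prescribe how it will be reported. Nothing rules out percentages or rates, adherence will be reported beside the count, and the cited published protocol, not available here, may say more. This stands in part: the plan is silent rather than wrong. But the number is the only event summary that the document specifies, and showing adherence beside it leaves the reader to combine the two without an interval.

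Four stronger readings are tempting, and the documents do not support them.

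- A reader might infer that safety rests on the count alone. It does not: pain and fatigue scores are part of the same definition, and questionnaires are modelled over time. Those scores do not count falls or injuries, however, and are not related to exercise volume.
- A reader might take the 10-fold spread as the size of the problem. It depends on an assumed 30 min/week. The plan's own goals give 2-fold, and with 3 events the intervals at the two goals overlap heavily.
- A reader might infer that exercise hours are already in hand. A screenshot follows each session, and the app records average heart rate. The document does not say that the screenshot shows duration, that events are timed against sessions, or that events in the wait period are recorded.
- A reader might infer that equipment faults are counted as adverse events. Technology and telehealth challenges are a separate metric in the same section.

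It is also fair to object that a rate per hour is no neutral standard. People who stop because of discomfort add few hours, so those who tolerate the programme dominate the denominator. Events per participant offered the programme is a legitimate intent-to-treat summary. That is a reason to report both, not a reason to leave out exposure.

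**Conclusion.** The point holds as a gap in the planned summary. The adverse-event part of safety is given only as a number, exercise volume is self-chosen, and adherence is unknown in advance, so a low count cannot distinguish safe exercise from little exercise. The supported size is a 2-fold difference in event rate between the plan's own goals, which rests only on 12 weeks at 150 or 300 min/week. Larger differences are possible if adherence falls short, but they depend on assumed volumes. The rates in the table also depend on the assumed 20 exercisers and 3 events.

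The severity is minor. The trial is an exploratory pilot and no decision rule is tied to the count. The documents do not support saying that the safety result is invalid or that a rate has been ruled out.

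**What to change.** Keep the count and the pain and fatigue scores, and add two summaries.

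1. By arm and by period (intervention, and wait where events were recorded): the number and percentage of participants with at least one event, with an exact 95% CI.
2. During the intervention: events per logged exercise session, or per 100 logged hours if the session records show duration. Use an interval that allows for repeated events in one participant, such as a participant-level bootstrap or a Poisson model with robust standard errors. If there are no events, neither of these gives a useful interval; report the exact upper limit instead, as in the working.

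State which records supply the denominator, and whether events in the wait period were collected. If they were not, say so and give only the intervention period.

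The first summary needs only the participant and the period for each event. The second needs a tally of session records, and hours are possible only if duration was captured. Information on duration or event timing that was not collected at the time may not be recoverable.

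Two limits should be stated with the result. Missed screenshots understate exposure and raise the rate, by an unknown amount. Participants who stop early contribute little exposure, so the rate should always be read with the percentage of participants affected.

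### The primary mixed model gives each randomised arm its own baseline mean, so its change contrast is unbiased but usually less precise than a baseline-adjusted one

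*Combined protocol and SAP*

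**What the plan says.** Under Analyses, Primary Aim, the efficacy outcomes are analysed "using linear mixed-effects models to compare between-and within-group changes (IS or WC"). The mean structure is: "Models included fixed effects for the treatment group (IS vs. WC), time (baseline, week 7, and week 13), and their interaction". The covariance enters through participants: "Random effects were included for participants to account for individual variability". Akaike's criterion is used to choose the model, but the candidate models are not listed. Missing outcomes are handled by the mixed model, supplemented by multiple imputation.

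On allocation, the section on randomization and sample size says: "Participants were randomized with a 1:1 allocation ratio using a permuted block randomization approach".

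The documents state no baseline covariate, no common-baseline constraint and no other baseline adjustment. They also give no sample size, SD or correlation.

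**The concern.** Randomisation makes the two baseline means equal in expectation. A model with a group main effect and baseline as a time level does not use that fact. It estimates a separate baseline mean for each arm and subtracts it from that arm's week-13 mean, which is the same as fixing the regression slope of week 13 on baseline at 1. If the true slope is below 1, this subtracts too much of the chance baseline difference and adds noise.

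What is at stake is interval width. The Analyses section says that the findings are to inform the size and design of a later effectiveness trial, so the estimates and their intervals are the pilot's main quantitative product. Intervals wider than the collected data require make that product less useful.

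**Working it through.** **Inputs.** From the documents: the model terms, the visits (weeks 0, 7 and 13) and 1:1 allocation. Assumed, because the documents do not give them: n = 15 per arm, r = 0.3 to 0.9 (correlation of baseline with week 13), and k = baseline SD / week-13 SD. The plan states no figure that could be reproduced.

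**Step 1: what the contrast is.** Group, three-level time and their interaction give a free mean for each arm at each visit. With complete data the week-13 interaction must then be the difference between arms in mean change. A random-intercept fit to three simulated data sets (17 per arm; r = 0.3, 0.6, 0.9) gave 0.6690, -0.3538 and 0.1562. Each equals the raw change difference to at least 14 decimals.

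**Step 2: variance.** In units of (week-13 variance) × (2/n):

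- change contrast: 1 + k² - 2rk
- adjusted contrast with estimated slope: (1 - r²) × (1 + 1/(2n - 4))

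Since 1 + k² - 2rk = (1 - r²) + (k - r)², the ratio of change to adjusted variance is [1 + (k - r)²/(1 - r²)] / (1 + 1/(2n - 4)). This assumes normal data with the same slope and residual variance in both arms.

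At n = 15 the slope-estimation factor is 1 + 1/26 = 1.0385. Example, k = 1 and r = 0.5: change 1 + 1 - 1 = 1.000; adjusted 0.75 × 1.0385 = 0.779; ratio 1.284.

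| r | k = 1 | k = 0.7 | k = 1.3 |
|---|---|---|---|
| 0.3 | 1.481 | 1.132 | 2.021 |
| 0.5 | 1.284 | 1.014 | 1.785 |
| 0.7 | 1.133 | 0.963 | 1.643 |
| 0.8 | 1.070 | 0.990 | 1.632 |
| 0.9 | 1.014 | 1.166 | 1.774 |

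A three-visit simulation (40,000 replicates per cell) agreed with this formula within 0.015, and mean estimates were within about 0.01 of zero under no effect.

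**Step 3: worst case for adjusting.** The ratio is smallest at k = r, where the true slope is 1. It is then 1/(1 + 1/(2n - 4)) = 0.941, 0.963 and 0.973 at 10, 15 and 20 per arm. The extra variance from adjusting is therefore at most 1/16 = 6.3%, 1/26 = 3.8% and 1/36 = 2.8%.

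**Step 4: interval width.** If the random effect is an intercept only, the written model pools its residual over visits: 28 × 2 = 56 degrees of freedom at 15 per arm. A per-visit analysis of covariance has 27. The expected width ratio is √(variance ratio) × t(56)/t(27) × a small correction for the expected value of the estimated SD. Here t(56)/t(27) = 2.003/2.052 = 0.976 and the correction is 0.9955/0.9908 = 1.005. For k = 1:

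| r | width ratio, written / adjusted |
|---|---|
| 0.3 | 1.217 × 0.976 × 1.005 = 1.19 |
| 0.5 | 1.133 × 0.976 × 1.005 = 1.11 |
| 0.7 | 1.064 × 0.976 × 1.005 = 1.04 |
| 0.8 | 1.034 × 0.976 × 1.005 = 1.015 |
| 0.9 | 1.007 × 0.976 × 1.005 = 0.99 |

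**Step 5: where the gain may vanish.** For the Godin questionnaire, entry is restricted: "People were excluded if they were physically active (>150 minutes per week of moderate-to-vigorous intensity exercise in a typical week"). The intervention then aims higher: "with a minimum goal of 150 min/week of moderate-intensity exercise and an advanced goal of 300 min/week of moderate-intensity exercise". A baseline SD below the week-13 SD is therefore plausible, though this is an inference. At k = 0.7 and r = 0.5 to 0.8 the ratio is 0.96 to 1.01, so there is essentially no gain.

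**Step 6: a remedy to avoid.** A common baseline mean combined with a random intercept alone does not have the bound in step 3. Simulated ratios at k = 0.7 were 1.15, 1.00, 0.90, 0.86 and 0.83 for r = 0.3, 0.5, 0.7, 0.8 and 0.9, so it can lose precision.

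**Step 7: missing values.** With 15% of values missing completely at random, the written model relative to an unstructured common-baseline model gave 1.53, 1.26, 1.16 and 1.08 at k = 1 (r = 0.3, 0.5, 0.7, 0.8). The plan's multiple imputation was not simulated.

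**The case against.** The written model is a standard one, and nothing in it is invalid or contradictory. The Analyses section says that the pilot is not powered for effectiveness, so no efficacy decision depends on interval width. Every size above rests on assumed inputs, and over the assumed range the variance ratio runs from 0.96 to 2.02. The written model's pooled degrees of freedom win back part of the loss. All of this stands, and it keeps the point at the level of an optional improvement. It does not remove the point: the baseline values are already collected, and the worst cost of adjusting is small and bounded.

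A reader might infer more than the documents support:

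- *That the estimates are biased by baseline imbalance.* They are not. Over randomisation the change contrast is unbiased.
- *That a later trial would be underpowered.* The documents do not commit a later trial to this contrast. One sized on it would, where the contrast is less precise, ask for more participants than needed.
- *That the choice by Akaike's criterion excluded an adjusted model.* No candidates are listed at all, so the silence shows little.
- *That these sizes apply to whatever is reported.* The post hoc sentence reads: "Post hoc analyses were conducted using least-squared mean differences and 95% confidence intervals (CI"). It does not say whether the difference is a change contrast or a week-13 contrast. That is a separate missing detail. The figures here cover only the change contrast, the reading favoured by the stated aim of comparing changes.

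**Conclusion.** The point holds as a matter of efficiency. With complete data, or within each fully imputed data set, the written change contrast is the raw difference in mean change: valid, but usually less precise than a baseline-adjusted contrast when SDs are similar over time and r is low to moderate. At an assumed 15 per arm and equal SDs, the excess variance falls from about 48% at r = 0.3 to about 1% at r = 0.9. The interval penalty falls from about 19% to nothing, with a slight reversal at r = 0.9. The interval figures also assume a random intercept with pooled residual degrees of freedom. A uniform gain across outcomes is not supported: for the activity questionnaire it may be nil. Severity is low: the sponsor could make this change, but the plan is not wrong without it.

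**What to change.** Fit the post-baseline values with group, time, group-by-time, baseline and baseline-by-time. The participant random effect can stay. Impute a missing baseline under the planned multiple imputation.

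Alternatively, fit a constrained longitudinal model (time and group by post-baseline time, with a common baseline mean) with an unstructured covariance and Kenward-Roger degrees of freedom. This keeps participants whose baseline is missing, for example after a late blood spot is excluded. The two models are close, but not identical when baselines are missing. Do not pair the common-baseline constraint with a random intercept alone.

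Report the adjusted week-13 difference between arms with its 95% interval. For the activity questionnaire ("Self-reported activity was measured via the Godin Leisure Time Exercise Questionnaire (GLTEQ) at weeks 0, 7, and 13"), also report the baseline and week-13 SDs, so that readers can see whether adjustment helped.

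Cost: no new data, and a changed model statement. The Primary Aim text is in the past tense, so the written model may already have been run. In that case report the adjusted result alongside it, labelled as added; this means a second set of estimates for about eight cardiometabolic and activity outcomes. The statistical downside is at most about 4% extra variance at 15 per arm (about 6% at 10) when the true baseline slope is near 1, and possibly fewer residual degrees of freedom.
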